9.4.1 General Considerations

Disposition, analysis populations, demography, baseline characteristics, medical history, and concomitant medication data will be summarized overall and by treatment, where applicable.

Efficacy endpoints will be summarized by treatment and visit. For the efficacy endpoints that are collected longitudinally, a last observation analysis will be performed by carrying forward the last post-baseline assessment. These last observation carried forward (LOCF) analyses guarantee the maximum number of randomized patients who were assessed post-baseline will be included in the analyses. In addition, for continuous efficacy endpoints, mixed effect model repeated measures (MMRM) analyses will be performed to mitigate the impact of missing data, which will be assumed to be missing at random during the study. Continuous and score data will be summarized using descriptive statistics (eg, mean and standard deviation or standard error). Categorical and dichotomous data will be summarized using frequency tables (counts and percentages).

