9.4.6 Efficacy Analyses

The primary endpoint (percent change from baseline in EASI total score) will be analyzed using a mixed model for repeated measures (MMRM). The model will include fixed effect for study treatment (TER-101 2.75%, vehicle), visit day (Day 15, Day 29), and treatment-by-visit interaction, with visit as the repeating factor, subject as a random effect, and baseline score as a covariate. The treatment p-value (TER-101 2.75% vs. vehicle), treatment difference, and 95% confidence limits from the model will be presented for the percent change from baseline in EASI at Day 29. Sensitivity analyses will include analysis of covariance (ANCOVA) at each timepoint. The impact of dropouts and missing data on results for the primary endpoint will be explored using the last value carried forward (LOCF) and multiple imputation methods, as appropriate.

Secondary efficacy endpoints that are continuous variables (percent change from baseline in EASI component scores, absolute change from baseline in EASI, IGA, TBSA, and WI-NRS) will also be analyzed using the MMRM model, as described above. In each case, the treatment p-value (TER-101 2.75% vs. vehicle), treatment difference, and 95% confidence limits from the model, will be presented.

The effect of treatment on response rates (75% reduction in EAI Score [EASI-75], 50% reduction in EASI scores [EASI-50]) at each visit will be evaluated using a logistic generalized linear mixed model (GLMM) for binary data, with fixed effect for treatment, visit and treatment-by-visit interaction. The treatment p-value (TER-101 2.75% vs. vehicle), treatment odds ratio, and 95% confidence limits from the model, will be presented. [Note: In the event of model non-convergence, the response proportions will be analyzed using the Cochran-Mantel-Haenszel test, stratified by baseline IGA.] The proportion of WI-NRS responders (defined by a reduction of ≥ 3 in subjects with baseline WI-NRS ≥ 4) will be analyzed using a chi-square test.

Time to onset of response (EASI 75, EASI-50) will be estimated using the Kaplan-Meier method, with treatment comparisons based on the logrank test. Subjects who do not achieve response criteria will be censored on the day of last assessment.

Given the exploratory nature of this study, p-values from all significance tests will be reported without adjustment for multiplicity.

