3.6.1 EASI Analyses

For each visit (baseline, Day 15, Day 29), the following analyses will be performed. All analyses will be based on the ES.

- Descriptive statistics (n, mean, Std Dev, median, minimum, and maximum) will be provided for the per-subject EASI total score (continuous), change from baseline, and percent change from baseline in EASI total score.
- Descriptive statistics (n, %) will be provided for the number and percentage of subjects who achieve EASI-50 (i.e., ≥50% reduction from baseline) and EAST-75 (i.e., ≥75%).

Descriptive statistics (n, mean, Std Dev, median, minimum, and maximum) will be provided for the per-subject EASI by region (head, trunk, upper extremity [UE], lower extremity [LE]), change from baseline, and percent change from baseline values. Treatment group comparisons

in percent change from baseline in EASI total score will be analyzed using a mixed model for repeated measures (MMRM). The model will include fixed effect for study treatment (TER-101 2.75%, vehicle), visit day (Day 15, Day 29), and treatment-by-visit interaction, with visit as the repeating factor, subject nested within the investigational site as a random effect, and baseline score as a covariate. The variance-covariance matrix will be assumed to be unstructured. If the procedure does not converge then the replacement of variance-covariance matrix will be explored in the order of Toeplitz, first-order autoregressive, compound symmetric. The treatment p-value (TER-101 2.75% vs. vehicle), treatment difference, and 95% confidence limits from the model will be presented for the percent change from baseline in EASI at Day 29. Similarly, the treatment difference (TER-101 2.75% vs. vehicle) and 95% confidence limits will be presented for Day 15 as well. Line graphs of least squares mean in percent change from baseline of EASI scores will be presented for Day 15 and Day 29. These treatment group comparisons will be repeated for the PPES.

The following sensitivity analyses will be conducted for the percent change from baseline in EASI total score at Day 29 to explore the impact of dropouts and missing data at Day 29.

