- Last value carried forward (LOCF): for timepoint Day 29, if missing, the last available post baseline EASI total score will be carried forward to the timepoint. After this imputation, an analysis of covariance (ANCOVA) will be used for analyzing the treatment effect at Day 29. The treatment group will be the fixed effect and baseline score will be the covariate. The treatment difference, 95% confidence limits, and p-value will be presented.
- Return to baseline: missing Day 29 value will be imputed based on the baseline value for the patient, with variance adjustment of the Day 29 EASI total score. That is, the missing data will be imputed with values from Normal distribution $N(\text{baseline}_i, \sigma_k^2)$; i = i th subject, where σ_k^2 is the variance estimate of treatment k at Day 29. Five hundred (500) imputation will be implemented. ANCOVA model will be used for each imputation. The results from all imputed datasets will be combined using Rubin's combination rule (PROC MIANALYZE).

In addition, the percent change from baseline in EASI scores and the absolute change from baseline in EASI total score by each region will be analyzed using the MMRM model, as described above. In each case, the treatment p-value (TER-101 2.75% vs. vehicle), treatment difference, and 95% confidence limits from the model, will be presented.

The effect of treatment on response rates (EASI-75, EASI-50) at each visit will be evaluated using a logistic generalized linear mixed model (GLMM) for binary data. The model will include fixed effect for treatment, visit and treatment-by-visit interaction, with subject nested within the investigational site as a random effect. The treatment p-value (TER-101 2.75% vs. vehicle), treatment odds ratio, and 95% confidence limits from the model, will be presented. [Note: In the event of model non-convergence, the response proportions will be analyzed using the Cochran-Mantel-Haenszel test, stratified by baseline IGA.] Bar charts of the response rates at Day 15 and Day 29 will be presented by treatment groups for each response rate (EASI-75, EASI-50).

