3.6.3 WI-NRS Analyses

Descriptive statistics (n, mean, Std Dev, median, minimum, and maximum) will be provided for the 11-point WI-NRS scale at baseline, Day 15 and Day 28 visits, and its change from baseline at Day 15 and Day 28. A line plot over time of the change from baseline (daily, and weekly average [see intervals specified below]) will be generated. Mean (\pm Std Dev) will be displayed at each time point. Change from baseline WI-NRS scale will also be analyzed using the MMRM model for Day 15 and Day 28 assessments. The model will include fixed effect for study treatment (TER-101 2.75%, vehicle), visit day (Day 15, Day 28), and treatment-by-visit interaction, with visit as the repeating factor, subject within the investigational site as a random effect, and baseline WI-NRS scale as a covariate. The treatment p-value (TER-101 2.75% vs. vehicle), treatment difference, and 95% confidence limits from the model, will be presented.

The proportion of WI-NRS responders (defined by a reduction of ≥ 3 in subjects with baseline WI-NRS ≥ 4) will be analyzed using a logistic regression. The odds ratio, and 95% confidence limits from the model, will be presented. The chi-square test p-value will also be provided. In addition, the number and percentage of subjects who respond during each weekly interval (defined by the maximum reduction between Day 2-Day 8, Day 9-Day 15, Day 16-Day 22, Day 23-Day 28) will be summarized and presented in a bar chart.

All analyses will be based on ES.

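### The EASI-50/75 responder model falls back to CMH only on non-convergence, so an arm with zero responders at a visit could be reported as a converged fit with an uninformative odds ratio and a Wald p near 1

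*SAP*

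**What the plan says.** SAP 3.6.1 evaluates the EASI-75 and EASI-50 response rates at each visit with a logistic generalized linear mixed model: "The model will include fixed effect for treatment, visit and treatment-by-visit interaction, with subject nested within the investigational site as a random effect". From it, the treatment p-value is to be reported, and the "treatment odds ratio, and 95% confidence limits from the model, will be presented". The only alternative is in a note: "In the event of model non-convergence, the response proportions will be analyzed using the Cochran-Mantel-Haenszel test, stratified by baseline IGA". Protocol 9.4.6 describes the same model, "with fixed effect for treatment, visit and treatment-by-visit interaction", with the same single trigger.

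Neither document has a rule for an arm with no responders or for an odds ratio that cannot be estimated. The SAP names neither the estimation method nor the type of test for this model.

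Two other provisions matter. SAP 3.6.1 also says: "Descriptive statistics (n, %) will be provided for the number and percentage of subjects who achieve EASI-50", and likewise for EASI-75, so a zero would be visible in the tables. For the other binary endpoint, the WI-NRS responders in SAP 3.6.3, a model-free result accompanies the logistic regression unconditionally: "The chi-square test p-value will also be provided". EASI-50/75 has no such companion.

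**The concern.** With the interaction in the model, each arm-by-visit combination has its own logit. If no vehicle subject responds at a visit, the likelihood keeps rising as the vehicle logit goes to minus infinity, so no finite maximum exists. The likelihood also flattens, so an optimizer can meet its stopping rule and report success. The fallback is tied to what the software reports, not to the event that breaks the estimate, so it may not start.

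The printed result could then be an enormous odds ratio, an interval that says nothing and a Wald p near 1. This would happen when vehicle response is absent, the situation most favorable to the drug. Protocol 9.1 says the analyses are to judge the drug's activity and potential for further study, and SAP 1.3 sends topline summaries to the sponsor for development planning. A p-value near 1 beside six responders against none would mislead that reading.

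**Working it through.** **Inputs.** SAP 1.2: about 60 randomized, 15% dropout, about 50 completing. The figures agree: 60 × 0.85 = 51, and 50 / 0.85 = 58.8, so 59. With 1:1 allocation (SAP 2) this is about 30 per arm randomized and 25 completing. I use 28 per arm as an assumed number assessed at a visit, with 25 alongside. SAP 3.1: two-sided 0.05. All response rates are assumptions, because the documents give none.

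**1. Chance of zero vehicle responders at a visit**, (1 − p)^n:

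| True vehicle rate | 3% | 5% | 10% | 15% | 20% |
|---|---|---|---|---|---|
| n = 28 | 43% | 24% | 5% | 1% | 0.2% |
| n = 25 | 47% | 28% | 7% | 2% | 0.4% |

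**2. What a fit does with a zero cell.** For 6/28 against 0/28 at one visit, one logistic routine reports convergence with standard error 15,017 and Wald p 0.999. Another reports non-convergence, which would trigger CMH. On the same data:
- Likelihood-ratio p = 0.003 and Fisher p = 0.023.
- Mantel-Haenszel, unstratified, with m = 6 responders in total: (6 − 3)² / [28² × 6 × 50 / (56² × 55)] = 9 / 1.364 = 6.6, so p = 0.010.

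A two-visit random-intercept model with 25 per arm behaves the same way. With vehicle 0 then 2 and active 6 then 8 responders, the optimizer reports success. The Day 15 log odds ratio is 18.6 with standard error 1,592 and p = 0.991, where Fisher gives 0.022. The Day 29 contrast stays estimable (p = 0.09). The visit-averaged contrast does not (p = 0.989). Changing vehicle to 1 then 2 makes every contrast finite. These fits were in Python; the SAP specifies SAS, which was not tested.

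**3. Worst-case power, single visit.** Sum Bin(a; n, active rate) × Bin(v; n, vehicle rate) over all counts a and v that reject. The Wald statistic is log[a(n − v) / (v(n − a))] divided by √(1/a + 1/(n − a) + 1/v + 1/(n − v)). It is counted as non-rejecting when an arm has 0 or n responders. In those cells, substitute Fisher or the asymptotic Mantel-Haenszel test. With n = 28:

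| Vehicle, active | Wald only | Fisher in those cells | Mantel-Haenszel in those cells |
|---|---|---|---|
| 5%, 25% | 28% | 46% | 51% |
| 10%, 25% | 20% | 24% | 25% |
| 15%, 25% | 11% | 12% | 12% |

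Check on the first row: 0.95^28 = 0.238. Zero vehicle responders together with at least 6 active responders, the number Fisher needs, has probability 17.5%, and 28.1% + 17.5% = 45.6%. With n = 25 the first two rows become 23% against 40-48% and 18% against 23-25%.

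**4. Type I error.** Over null rates of 1-50% with n = 28, the maximum is 4.5% for all three rules. With n = 25 it is 5.1% for all three, so the substitution does not move it. At a null rate of 5% (n = 28), the error rises from 0.03% to 2.4% with Mantel-Haenszel, still below 5%.

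**5. Baseline IGA.** In single-visit simulations (28 per arm, half IGA 2, treatment log odds ratio 1.3, 4,000 runs per setting), adjusting for IGA raises power from 61% to 65% if its prognostic odds ratio is 2, and from 55% to 62% if it is 4. Type I error is 5.0-5.5% either way.

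**The case against.** The harm needs four things at once: no vehicle responders, enough active responders for another test to detect a difference, software that reports convergence, and a Wald test. The SAP does not specify a Wald test, and a likelihood-ratio p-value would be sound, although the interval would still be uninformative. Some routines do flag the problem. Across 100 zero-cell datasets, success was reported in 73, 91 or 100 depending on the optimizer, so the existing fallback would sometimes work. A standard error in the thousands is also hard to miss beside tabulated counts. All of this stands. It makes the power comparison a worst case and the impact modest, but leaves the result dependent on an unstated software choice.

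A reader might infer from Protocol 2.3, which reports no placebo EASI-75 responders in the earlier study, that a zero cell is likely here. The documents do not support that. The earlier trial was shorter, in more severe disease, with 10 AD subjects randomized to vehicle. Zero of 10 has an exact upper 95% limit of 1 − 0.025^(1/10) = 31%. It shows only that a zero can occur.

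A reader might also take the missing baseline term as a source of bias. It is not: the unadjusted comparison is valid under randomization, and the protocol's model omits the term too.

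Finally, one might want an exact test in sparse cells. Its p-value can contradict a score interval. For 5 against 0 of 28, Fisher p is 0.051 while the Miettinen-Nurminen interval is 4.5 to 36 percentage points. For 4 against 0 they are 0.11 and 1.2 to 32.

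**Conclusion.** The gap is real but narrow. The trigger rests on reported convergence, while the failure comes from a zero (or full) arm-by-visit cell that a fit can pass through without complaint. It matters mainly for EASI-75 at a vehicle rate of about 5% or less, where the worst-case loss is 18 to 23 percentage points of power (28% against 46% or 51%). At 10% the loss is 4 to 5 points, and from 15% it is negligible. EASI-50 is hardly affected unless vehicle response is equally rare.

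These sizes assume 28 per arm, a single visit, a Wald test, a fallback that never fires and response rates the documents do not give. They are not the expected performance of the SAP's two-visit model in SAS. The endpoints are secondary, p-values are exploratory and unadjusted, counts are shown, and the primary EASI analysis is untouched. The change is worth making because it is cheap and removes an avoidable misleading result. The baseline term is a precision gain only.

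**What to change.** In SAP 3.6.1, before unblinding:

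(a) Extend the fallback note so that CMH stratified by baseline IGA applies on non-convergence, *or if either treatment arm has zero or all responders at a visit*, for the response proportions at that visit. The other visit stays with the mixed model unless that fails. For the affected visit, show the odds ratio as not estimable and give one prespecified score-based risk difference with its 95% interval, for example Miettinen-Nurminen stratified by baseline IGA, so that p-value and interval are of the same type. If both arms have zero responders, or both have all, give counts only.

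(b) Add baseline IGA as a covariate to the mixed model, so that the model and its fallback both adjust for it.

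The cost is two or three sentences, minor programming and an entry in SAP Section 4. The downside of (a) is that the asymptotic test is approximate in sparse tables; the enumeration that found maximum type I error unchanged used the unstratified version. Under (b), one more parameter in a sparse model may make non-convergence somewhat more frequent, which the fallback covers.

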3.6.2 IGA Analyses

Descriptive statistics (n, mean, Std Dev, median, minimum, and maximum) will be provided for the IGA scale, and its change from baseline at Day 15 and Day 29. Number and percentage of subjects for each scale value (0-4) will also be provided for each visit.

The change from baseline IGA values will be analyzed using generalized linear model for repeated ordinal data method. The multinomial distribution will be used with link function of cumulative logit. The model will include fixed effect for study treatment (TER-101 2.75%, vehicle), visit day (Day 15, Day 29), and treatment-by-visit interaction, with subject nested within the investigational site as a random effect, and baseline IGA scale as a covariate. The treatment p-value (TER-101 2.75% vs. vehicle), treatment difference, and 95% confidence limits from the model, will be presented. All analyses will be based on ES.

3.6.3 WI-NRS Analyses

Descriptive statistics (n, mean, Std Dev, median, minimum, and maximum) will be provided for the 11-point WI-NRS scale at baseline, Day 15 and Day 28 visits, and its change from baseline at Day 15 and Day 28. A line plot over time of the change from baseline (daily, and weekly average [see intervals specified below]) will be generated. Mean (\pm Std Dev) will be displayed at each time point. Change from baseline WI-NRS scale will also be analyzed using the MMRM model for Day 15 and Day 28 assessments. The model will include fixed effect for study treatment (TER-101 2.75%, vehicle), visit day (Day 15, Day 28), and treatment-by-visit interaction, with visit as the repeating factor, subject within the investigational site as a random effect, and baseline WI-NRS scale as a covariate. The treatment p-value (TER-101 2.75% vs. vehicle), treatment difference, and 95% confidence limits from the model, will be presented.

The proportion of WI-NRS responders (defined by a reduction of ≥ 3 in subjects with baseline WI-NRS ≥ 4) will be analyzed using a logistic regression. The odds ratio, and 95% confidence limits from the model, will be presented. The chi-square test p-value will also be provided. In addition, the number and percentage of subjects who respond during each weekly interval (defined by the maximum reduction between Day 2-Day 8, Day 9-Day 15, Day 16-Day 22, Day 23-Day 28) will be summarized and presented in a bar chart.

All analyses will be based on ES.

3.6.4 TBSA Analyses

The TBSA involved with AD at baseline, Day 15, and Day 29 will be summarized descriptively (n, mean, Std Dev, median, minimum, and maximum). The change from baseline values will also be analyzed using MMRM method. The model will include fixed effect for study treatment (TER-101 2.75%, vehicle), visit day (Day 15, Day 29), and treatment-by-visit interaction, with visit as the repeating factor, subject as a random effect, and baseline TBSA as a covariate. The treatment p-value (TER-101 2.75% vs. vehicle), treatment difference, and 95% confidence limits from the model, will be presented. All analyses will be based on ES.

3.7 SAFETY ANALYSIS

The safety and tolerability of the investigational product will be determined by local tolerability assessment, reported AEs, laboratory tests, physical examinations, vital signs, and ECGs. The Safety analysis set with actual treatment received (as opposed to randomized treatment) will be used for all safety summaries, unless otherwise specified.

3.7.1 Study Drug Exposure And Compliance

Duration of treatment (Last study treatment application date – First study treatment application date + 1) will be summarized descriptively for the SS. Study drug compliance will be assessed based on subject reports in the e-diary. The number of actual treatment applications as a percentage of the number of expected applications will be summarized. The usage of ointment (dispensed kit weight – returned kit weight) and average daily use (g) will also be summarized by treatment group.

3.7.2 Local Tolerability

For each visit (baseline [pre-dose, post-dose], Day 15, Day 29), the number and percentage of subjects with grades 0, 1, 2, 3 will be tabulated at timepoints specified for erythema and

symptoms of burning/stinging or pruritus associated with study drug application. In addition, severity grades will be summarized using a shift table based on the baseline pre-dose value at each visit. Severity grade shift from pre-medication at baseline to post-medication will be analyzed. The shift from pre-dose severity grade at baseline to the last post-dose severity grade will also be summarized by treatment groups for erythema, burning/stinging, and pruritus.

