Study drug application		X				1 st dose of study drug will be applied by site staff and the subjects instructed on application. All subsequent application will be at home through evening dose on Day 28.
Dispense study medication, Instructions for Use, e-diary		X		[X]		Study drug will be weighed at the Baseline Visit, prior to first dose. Additional study drug may be dispensed on Day 15 if needed.
Instruct on WI-NRS tool		X	X	X		
Review e-diary, WI-NRS for compliance			X	X	X	The e-diary will be reviewed at each visit.
Collect and weigh study drug.				X	X	Study drug (used and unused tubes) will be collected and weighed at in person visits on Day 15 and Day 29. Study drug will be returned to subject at Day 15 and not returned to subject at Day 29.

AE=adverse event; BID = twice daily; D = Day; e-diary = electronic diary; EASI = Eczema Area and Severity Index; ECG= electrocardiogram; IGA = Investigator Global Assessment; PK = pharmacokinetics; TBSA = Total Body Surface Area; WI-NRS = Worst Itch Numeric Rating Scale.

^aETV: Early Termination Visit. All assessments scheduled for Day 29 will be conducted in event subject early terminates from study.

^bClinical labs: Complete blood count with differential, chemistry will be conducted at screening, baseline, Day 29. Urinalysis will be conducted at screening only. If the clinical laboratories were obtained within 14 days of baseline (Day 1), the screening labs will be used as the baseline labs and do not need to be repeated.

^cThe screening ECG will be used as the baseline ECG.

^dPK blood draws should be done at least 4 hours after last study drug application. The date, time of last application will be recorded on electronic case report form page. Avoid drawing PK samples through study drug application site.

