6.2 Dose Modification

If a subject develops severe local application site adverse effects or a total skin tolerability score > 7, treatment will be held at that treatment site until the local AE resolves or skin tolerability score returns to baseline. The subject may then reinitiate application of study drug once daily to that site. Any interruptions in study treatment will be recorded, as well as the discontinuation date, restart date, and reason for discontinuation. The reason for discontinuation will also be recorded as an AE (See [Section 8.3](#) for additional information on AEs and SAEs). If the subject continues to experience signs and symptoms of treatment-related AEs, and the discomfort is

intolerable and continues despite decreased frequency of study treatment application, then the study treatment may be discontinued completely, at which time the subject will be discontinued from the treatment period (Day 1 to Day 29). See [Section 7](#) for additional information on discontinuation of study intervention.

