3.7.3 Adverse Events

All AEs will be coded and summarized using the Medical Dictionary for Regulatory Activities (MedDRA) (version 23.1). Treatment-emergent AEs (TEAEs) are defined as any new or worsening events reported at any time from the date of first dose of study medication until the end of study participation. All AEs will be presented in by-subject data listings, including the verbatim and coded terms, onset day (relative to start of treatment), severity, relationship to study medication, action taken, and outcome.

An overview of AEs for the SS will be provided, summarizing the frequency/incidence of the following:

- Incidence of all AEs;
- Count of TEAEs;
- Incidence of TEAEs;
- Count of Treatment-emergent SAEs (TESAEs);
- Incidence of TESAEs;
- Incidence of TEAE by maximum severity;
- Incidence of TESAE by maximum severity;
- Incidence of TEAEs that lead to discontinuation of study treatment;
- Incidence of TESAEs that lead to discontinuation of study treatment;
- Incidence of TEAEs that lead to interruption of study treatment;
- Incidence of TESAEs that lead to interruption of study treatment;
- Incidence of Treatment-related TEAEs;
- Incidence of Treatment-related TESAEs.

The number and percentage of subjects with AEs will also be summarized by System Organ Class (SOC) and Preferred Term (PT) for the following categories:

- Incidence of TEAEs;
- Incidence of TESAEs;
- Incidence of TEAEs by maximum severity;

- Incidence of TEAEs that lead to discontinuation from study treatment;
- Incidence of TEAEs that lead to interruption from study treatment;
- Incidence of Treatment-related TEAEs.

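### The only cross-visit tolerability summary in SAP 3.7.2 stops at each subject's last grade; a shift to the worst grade should be added beside it

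*SAP*

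**What the plan says.** Erythema, burning/stinging and pruritus are each graded 0 to 3 before the first dose, about 15 minutes after it, and on Days 15 and 29 (Protocol 1.3 and 10.7; SAP 2.4.3.1). Each grade is an average over all application sites.

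SAP 3.7.2 plans four displays:
- By visit, "the number and percentage of subjects with grades 0, 1, 2, 3 will be tabulated at timepoints specified".
- Also by visit, "severity grades will be summarized using a shift table based on the baseline pre-dose value at each visit".
- A shift from before to after medication, which I read as the 15-minute comparison.
- Across visits, "The shift from pre-dose severity grade at baseline to the last post-dose severity grade will also be summarized by treatment groups".

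No shift to the worst or maximum grade is listed.

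Protocol 6.2 sets what happens after a severe local reaction: "treatment will be held at that treatment site until the local AE resolves or skin tolerability score returns to baseline". It continues: "The subject may then reinitiate application of study drug once daily to that site". It also states: "The reason for discontinuation will also be recorded as an AE". On the AE side, SAP 3.7.3 includes "Incidence of TEAEs that lead to interruption of study treatment", both in the overview and by SOC and PT, as well as TEAEs by maximum severity.

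Protocol 9.4.7 asks for a count and percentage, by arm, of subjects with local tolerability symptoms.

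**The concern.** The last grade answers how the subject's skin was at the end. For a safety summary, the first question is usually how bad it became. Here the two can differ for a reason built into the design: a reaction that triggers a hold keeps the site untreated until it settles, so severe grades tend to move back towards baseline before the final reading. The table that condenses each subject across visits is then the one most affected by recovery. If one arm has more reactions that recover, the comparison between arms in that table is blunted too.

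Tolerability is a secondary objective, and Protocol 2.3 names local application site events as the most likely TEAEs. A reader will want a plain per-subject count of severe grades, and the tolerability section does not provide one.

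**Working it through.** The plan states no tolerability rate, so there is no figure to reproduce. The check compares what each planned table can show, then gives an illustration.

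**1. The last-grade table against the Day 29 table.** For every subject with a Day 29 grade, the last grade is the Day 29 grade. Early termination assessments share the Day 29 column of the Schedule of Activities. The last-grade shift therefore differs from the Day 29 shift only for subjects whose final grade was taken at 15 minutes or on Day 15. It largely repeats a table already planned.

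**2. By-visit tables do not give the number ever affected.** If *a* subjects have grade 3 at 15 minutes and *b* have it on Day 15, the number with grade 3 at either time lies between max(*a*, *b*) and *a* + *b*. With *a* = *b* = 2, that is 2, 3 or 4 subjects. The by-visit counts cannot say which.

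**3. Effect of recovery on the last-grade shift.** About 60 subjects randomized 1:1 gives 60 / 2 = 30 per arm. Let *h* subjects have grade 3 on Day 15, up from a lower pre-dose grade. Let a fraction *f* of them be back at their pre-dose grade at the last assessment. Both *h* and *f* are assumptions; the documents give neither.
- Worst-grade shift to grade 3: *h* / 30, whatever *f* is.
- Last-grade shift to grade 3 (expected): *h*(1 − *f*) / 30.

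| *h* | Worst grade | Last, *f* = 0 | Last, *f* = 0.5 | Last, *f* = 1 |
|---|---|---|---|---|
| 1 | 3.3% | 3.3% | 1.7% | 0.0% |
| 3 | 10.0% | 10.0% | 5.0% | 0.0% |
| 6 | 20.0% | 20.0% | 10.0% | 0.0% |

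In every row the planned Day 15 shift table also shows *h* / 30, because these reactions are present on Day 15.

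**4. Whether the AE tables supply the missing count.** They do so only in part. The synopsis triggers a hold at grade 3 on two or more subscores; Section 6.2 triggers it at a total above 7. Both also do so for a severe local AE. With a single grade 3, the largest possible total is 3 + 2 + 2 = 7, which is not above 7. An isolated grade 3 therefore meets neither score trigger, and it enters the interruption table only if it leads to a hold by another route. AE intensity is also a different scale: Protocol 10.3.3 grades it by interference with everyday activities, whereas Protocol 10.7 grades the sign or symptom itself. Protocol 10.3.1 further excludes expected signs of the studied disease from AEs unless they are more severe than expected.

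A side observation: of the 4 × 4 × 4 = 64 subscore combinations, 10 meet the synopsis trigger and 4 meet the Section 6.2 trigger, all 4 among the 10. Those two passages must be reconciled. The point made here is the same under either.

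**The case against.** The strongest reply is that the last-grade shift is a supplement. The sentence that introduces it comes after by-visit counts and by-visit shifts, and those show in full any reaction present at 15 minutes or on Day 15. Holds are recorded as AEs with interruption and restart dates, and SAP 3.7.3 tabulates TEAEs leading to interruption and TEAEs by maximum severity, which are per-subject summaries. This stands. A reader might infer that severe local reactions disappear from the safety report; the documents do not support that.

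A reader might also infer that the last grade is bound to look mild. It is not. Restart can bring recurrence, a hold can still be unresolved on Day 29, and a subject who stops for tolerability is meant to have the Day 29 assessments at an early termination visit (Protocol 7.1). Holds apply to one site while grades average over all sites, so recovery at the held site need not return the recorded grade to baseline.

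A third tempting argument is that dosing is over by the last reading, since "All subsequent application will be at home through evening dose on Day 28". It is weak. Day 29 is nominally the day after the last dose, and the ±3-day window allows visits from Day 26. Burning/stinging and pruritus are asked about in relation to the last application (Protocol 8.3.4). Only inspected erythema could plausibly fade, so this point does not rest on that argument.

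Finally, end-of-treatment status is a fair question in its own right, which argues for keeping the last-grade table. A worst grade will also pick up some fluctuation in the underlying AD, which Protocol 8.3.4 asks assessors to separate from tolerability as far as possible.

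**Conclusion.** The point holds as a minor, inexpensive improvement to a descriptive section. A severe reaction that recovers can show as no change in the last-grade shift, and no planned tolerability table counts the subjects who ever reached each grade. That per-subject count is also the natural reading of Protocol 9.4.7, although the synopsis describes tolerability summaries by treatment and visit.

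The size cannot be fixed from the documents. For any given number of grade 3 reactions, the last-grade table may show all of them, none, or anything between. The ranges in the working rest on assumed reaction and recovery rates, and neither end is an expected value. The efficacy analyses are unaffected, and so is the reporting of holds as AEs. A worst-grade shift would still miss a reaction that arose and resolved between graded assessments, and it would not undo the averaging over sites.

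**What to change.** Add one display to SAP 3.7.2 and keep the by-visit tables and the last-grade shift. Suggested content: for erythema, burning/stinging and pruritus separately, a shift table by treatment group from the baseline pre-dose grade to the worst post-dose grade. The worst grade is taken over 15 minutes, Day 15, Day 29 or early termination, and any unscheduled grade if one is recorded. The Schedule of Activities plans no unscheduled tolerability assessments, so that last element may be empty.

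The cost is one extra descriptive table from data already collected. Its drawback is that a worst grade partly reflects fluctuation in the underlying AD; both arms are graded on the same schedule, and a footnote can say so. Specify it before database lock so that the choice of summary is not made after unblinding.
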